14.2 Qualitative analysis

Qualitative data collected through semi-structured interviews and focus groups will be audiorecorded, transcribed, and coded. Field notes from observations and free text entries in logbooks will be coded using a similar system. An inductive approach will be used to analyse the data, drawing on grounded theory techniques including the constant comparison approach to identify constructs and themes which will influence the emerging theory. In addition to inductive findings elicited via thematic analysis, the qualitative coding will use deductive a priori starting codes which reflect concepts in the research questions and used as a framework to organise and initiate qualitative analysis. Analysis will also be guided by the realist approach,[80] identifying how contextual characteristics interact with mechanisms of action configurations to impact outcomes. We will also use the interviews and focus groups to explore how contextual factors (e.g. population, setting, wider environment characteristics) may have affected implementation of the intervention. We will also explore how contextual factors interact with proposed mechanisms of action to shape implementation and affect outcomes.

The qualitative research will aim to explore intervention mechanisms and how these interact with context, for example FE context and student characteristics, to lead to outcomes. Informed by realist approaches [80,81] we will consider potential mechanisms of action for the intervention, and how these interact with contextual factors, leading to intended and unintended effects. We will develop context-mechanism-outcome (CMO) configurations around key elements of the intervention and use these to develop topic guides for interviews and focus groups. Interviews and focus groups will therefore be theory-driven yet will retain sufficient flexibility to respond to emergent findings. Qualitative data on context, mechanisms and factors influencing implementation will be collected via: telephone interviews with trainers; student surveys; telephone interviews with trained staff and focus groups with students. For example, we will test hypotheses relating to the impact of teacher workload on the fidelity of delivery of staff training and subsequent use of training.

Development and Evaluation of Complex Interventions for Public Health Improvement A UKCRC Public Health Research Centre of Excellence

14.3 Cost effectiveness analysis

The pilot cRCT will examine whether it is feasible to assess cost effectiveness within a Phase III trial and provide information to inform its design. Our plan for this will proceed in five parts. We will cost the intervention, using logbooks and records of intervention delivery, collected at both feasibility and pilot cRCT stages, to measure resource use. This will include asking staff to record the time spent being trained along with their salary spine points to estimate costs. These would be combined with unit costs assembled from standard sources (such as NHS reference costs [82] and the Personal Social Services Research Unit Compendium [83]) to estimate the cost of the intervention. Second, we will refine and test a resource use questionnaire for this setting, drawing on those used in similar school-based sexual health intervention trials. This will capture resource use of health and social services to better understand cost differences that might accrue to broader health and social services.

The resource use questionnaire will be administered at baseline and follow-up in the pilot cRCT. We will assess the completeness and distribution (e.g. floor and ceiling effects) of responses and carry out a descriptive comparison of responses between arms, to assess the acceptability of the questionnaire and its likely ability to capture the impact of the intervention on the use of relevant services. Third, we will explore the appropriateness and feasibility of capturing the benefits of the intervention using the EQ-5D-5L measure. We will use published tariffs from the UK population to estimate health-related quality of life from EQ-5D-5L. We will use differences between intervention and control schools to consider the feasibility and relevance of the EQ-5D-5L in determining potential impacts of the intervention in the FE setting. Fourth, we will undertake a qualitatively-led valuation and costing exercise as part of our process evaluation to identify potential benefits and cost domains that are not captured adequately by the EQ-5D-5L or by the resource use questionnaire. Fifth, we will examine whether linkage to routine data could provide long-term health and social services data.

We will determine whether an economic evaluation will be feasible based on a) the completeness and distributional characteristics of data obtained through direct costing and questionnaire use, b) the resource use questionnaire, and c) the identifying relevant cost and benefit domains through process evaluation. We will determine, based on EQ-5D-5L responses, whether a cost-utility analysis would be feasible or, if not, what the appropriate measure of effectiveness would be for a costeffectiveness analysis. We will also determine whether there are important consequences of the intervention which would not be captured using the instruments described above, such that an additional valuation exercise (e.g. a discrete choice experiment) would be appropriate for the main trial. If so, the qualitative work we will carry out will inform the choice of attributes to be included in such a valuation exercise. It will also inform development of the final version of the resource use questionnaire to be used in the main trial. We will use the process evaluation during the pilot cRCT to give an indicative estimate of an appropriate time horizon to be used in a Phase III trial.

15. Data Management

Quantitative and qualitative data will be managed by project staff using secure data management systems and stored anonymously using participant identification numbers. Quantitative data will be managed by the Centre for Trials Research (CTR) at Cardiff University, a fully accredited registered clinical trials unit (CTU). Completed questionnaires will be transported or couriered to CTR by Trial Manager(s). All data will be stored in password-protected folders with user access restricted to those on the project.

Development and Evaluation of Comp

Interventions for Public Health Improvement

A UKCRC Public Health Research Centre of Excellence

Qualitative data will be managed by the SaFE Study Manager. Data will be stored securely in paper and/or electronic format, as appropriate. Data stored in paper format will be held securely at CU, in a locked room, in a locked cupboard or cabinet. Electronic data will be held securely in folders on CU servers and be accessed via username and password with access restricted to members of the research team. Digital recordings of interviews and focus groups will be stored securely, and will be held separately from transcripts and information on participant identities. Audio of interviews will be transferred securely and professionally transcribed, with transcripts then anonymised and entered into password-protected university files.

Identifiable data (paper-based and electronic) will be stored separately from non-identifiable source data. Access to identifiable data will be restricted to certain members of the research team. Those researchers with access to identifiable data will be responsible for anonymising the data before sharing with other members of the research team.

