6.1 Design

Intervention optimisation, feasibility testing and a pilot cRCT with integrated process and economic evaluations (MRC complex intervention phase II study).

Stage 1: Optimisation of training and publicity materials and an intervention manual for the SaFE intervention;

Stage 2: Feasibility testing in two FE settings followed by a period of refinement of the interventions; Stage 3: 2-arm pilot trial with cluster randomisation (at the level of FE setting) in 6 FE settings in England and Wales with an embedded process evaluation.

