7.1 Setting inclusion and recruitment

Phase 1: Intervention optimisation: Optimisation of intervention materials (manual, staff training and publicity materials) for use in FE settings with stakeholders, FE students, staff and ALPHA youth group. Recruitment of the participating FE setting will commence prior to study commencement and the site will be purposively sampled based on location in South Wales; sites used in the MRC PHIND funded SaFE project will be excluded. A sample of staff and students with capacity to participate will then be recruited for group interviews. Students under age 16 will be excluded.

Phase 2: Intervention feasibility testing: One college and one 6th form will be recruited for feasibility testing (n=1 college in England, n=1 6th form Wales). FE settings will be purposively sampled based on location in South Wales and Bristol/South Gloucester/North Somerset. No random allocation will occur. Sites used in the MRC PHIND funded SaFE project or optimisation phase (Phase 1) as well as those with current onsite sexual health provision (e.g. STI testing) will not be eligible to take part. We will incentivise FE setting retention by making a payment of £250 at the end of the feasibility testing.

Phase 3: Pilot cRCT: All state funded FE settings including community colleges and 6th forms attached to secondary schools will be eligible to participate, including private and Welsh medium schools. Inclusion criteria: All students aged 16 and older enrolled at participating FE settings.

Exclusion criteria: No FE students aged 16 and older will be excluded. Fieldworkers will support participation for those with learning difficulties or poor English. Schools for those with learning disabilities will be excluded. For this study, settings with existing onsite service provision (e.g. STI testing) will also be excluded from the sampling frame.

Study population: SaFE is designed to be a universal intervention for all students attending FE settings. The majority of FE students are aged 16-24. We will incentivise FE setting retention by making a payment of £500 at the end of the study. In Wales, two colleges and one 6th form will be recruited, and in England two 6th forms and one college will be recruited.

	England	Wales
Feasibility testing	FE college (n = 1)	6th form (n=1)
Pilot cRCT	FE college (n = 1)	6th form (n=1)
	6 th form (n=2)	FE college (n=2)

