7.2 Randomisation

No randomisation will occur during Phase 1 or 2. In the pilot trial, randomisation will occur after all settings have completed baseline data collection. Clusters (settings) will be randomised to receive either the SaFE intervention or usual practice. Following baseline surveys (Sep/Oct 2020), the trial statistician will randomly allocate settings into 2 arms using a 2:1 ratio: SaFE delivered in 4 settings, and usual practice in 2. The allocation will be stratified by country and type of setting. Recruitment will take place between January and July 2020.

Development and Evaluation of Complex Interventions for Public Health Improvement A UKCRC Public Health Research Centre of Excellence

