12.3 Trial Specific Safeguarding requirements

We will take the steps outlined in the Cardiff University Safeguarding Policy to reduce the likelihood of any adverse events arising from the intervention or research. All intervention materials will be based on existing materials and will be approved by the stakeholder advisory group and TSC prior to use. Research and intervention activities will be delivered adhering to the ethical considerations. This pilot is not powered to test for intervention effects (positive or adverse), but qualitative data will be collected as part of the process evaluation to explore potentially harmful mechanisms.

The SaFE Study Manager will ensure that all fieldworkers are aware of the Cardiff University Safeguarding Policy as well as the Lone Worker Policy. On site at schools and FE colleges, the study will adhere to existing Safeguarding policies and procedures in, which will be identified by the SaFE Study Manager in advance of data collection. All participants will be advised that information they provide will be confidential unless they disclose something during data collection which suggests that they are at serious and immediate risk of harm, at which time study safeguarding processes will be implemented, including incident recording and escalation to the school/college Safeguarding Lead. For the purposes of this trial the following events will be considered as safeguarding issues that must be captured and reported to the SaFE Study Manager as soon as possible:

- Incidences of sexual abuse involving immediate risk of harm;
- Grooming.
- Engagement in sexual practices in exchange for reparation (under age-18)

For the purposes of this trial the following events will not require reporting as safeguarding issues:

• Any planned treatments received by participants at the start of the trial.

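### Section 14.3 reads the relevance of the EQ-5D-5L, and in part the resource-use questionnaire's ability to capture impact, from arm differences that four versus two settings cannot support

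*Protocol*

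**What the plan says.** The design is a "2-arm pilot trial with cluster randomisation (at the level of FE setting) in 6 FE settings" (section 6.1). Settings are allocated "using a 2:1 ratio: SaFE delivered in 4 settings, and usual practice in 2" (section 7.2). On restriction, section 7.2 says: "The allocation will be stratified by country and type of setting". Section 7.1 fixes the mix: "In Wales, two colleges and one 6th form will be recruited, and in England two 6th forms and one college will be recruited".

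Section 14.3 brings arm differences into the assessment of two instruments. For the EQ-5D-5L: "We will use differences between intervention and control schools to consider the feasibility and relevance of the EQ-5D-5L in determining potential impacts". For the resource-use questionnaire, the team will "carry out a descriptive comparison of responses between arms". The stated purpose is to judge how acceptable the questionnaire is and whether it is likely to register the intervention's effect on service use. The same sentence also names completeness and floor and ceiling effects.

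Later in 14.3 come the decisions. Overall economic feasibility rests on completeness and distribution, on the resource-use questionnaire, and on the cost and benefit domains found by the process evaluation. For the type of analysis: "We will determine, based on EQ-5D-5L responses, whether a cost-utility analysis would be feasible". Neither statement names an arm difference.

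Section 14.1 calls the analyses mainly descriptive. It commits to examining completion, variability and floor or ceiling effects for the primary and secondary outcome measures; section 5.5 lists the EQ-5D-5L among the latter. Section 12.3 says: "This pilot is not powered to test for intervention effects (positive or adverse". Section 13.3 reports no power calculation. No section says what size of arm difference would count for or against either instrument.

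**The concern.** An arm difference on the EQ-5D-5L mixes three things: whether the intervention changed health-related quality of life, whether the instrument responds to such a change, and which settings happened to become controls. To read the second from the total, one must know the first and have the third under control. This pilot offers neither.

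A null result therefore cannot separate an insensitive instrument from an ineffective intervention or from chance. A non-null result cannot be separated from ordinary variation between settings. The design also leaves room for a null with a good instrument. Section 7.3 describes repeated cross-sections with high student turnover, and the synopsis gives a 10-month treatment period with follow-up at 12 months, so some follow-up respondents may have had little exposure.

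At stake is the advice to a Phase III trial on whether the EQ-5D-5L and the resource-use questionnaire are worth carrying forward. If the sentence in 14.3 is applied as written, a noisy difference could add weight for or against an instrument when it carries almost no information on the question.

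**Working it through.** The protocol gives no SD, intracluster correlation (ICC), cluster size or target difference for this comparison, so there is no figure of its own to reproduce. Two checks follow: the first uses protocol inputs only, the second rests on stated assumptions.

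**1. Allocation count (sections 7.1 and 7.2).** The six settings are one college and two 6th forms in England, and one 6th form and two colleges in Wales. Two become controls.

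- No restriction: C(6,2) = 15 allocations; smallest attainable randomisation p = 1/15 = 0.067.
- One control per country: 3 × 3 = 9; p = 1/9 = 0.111.
- One control per country and one per type: English college with Welsh 6th form, 1 × 1 = 1; English 6th form with Welsh college, 2 × 2 = 4; total 5; p = 1/5 = 0.20.

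The last two counts assume how the stratification will operate. Section 7.2 names only the factors, and section 13.1 leaves details to a separate randomisation plan. Under all three, no arm difference, however large, can reach p < 0.05 by a randomisation test.

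**2. Precision of the arm difference.** Cluster-level comparison, with m respondents per setting:

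SE (in SD units) = √{[ICC + (1 − ICC)/m] × (1/4 + 1/2)}, df = 6 − 2 = 4, t(0.975) = 2.776.

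Assumed, not in the documents: ICC 0.005 to 0.05, m 50 to 400, EQ-5D-5L index SD 0.15 to 0.20.

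Example, ICC 0.05 and m = 50: 0.05 + 0.95/50 = 0.069; × 0.75 = 0.05175; root 0.227; × 2.776 = 0.63 SD. The 95% half-widths in SD units are:

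| ICC | m = 50 | m = 100 | m = 200 | m = 400 |
|---|---|---|---|---|
| 0.005 | 0.38 | 0.29 | 0.24 | 0.21 |
| 0.01 | 0.42 | 0.34 | 0.29 | 0.27 |
| 0.02 | 0.48 | 0.42 | 0.38 | 0.36 |
| 0.05 | 0.63 | 0.59 | 0.56 | 0.55 |

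- On the index scale the range is 0.21 × 0.15 = 0.03 to 0.63 × 0.20 = 0.13. At m = 100 and SD 0.20 it is 0.068, 0.083 and 0.117 for ICC 0.01, 0.02 and 0.05.
- Over the same grid, the difference detectable with 80% power (noncentral t) is 0.28 to 0.86 SD. Power is 11% to 53% for a true difference of 0.2 SD and 6% to 18% for 0.1 SD.
- More students help little when the ICC is not small. At ICC 0.05, going from 50 to 400 per setting narrows the half-width only from 0.63 to 0.55 SD. With unlimited students it is 2.776 × √(0.05 × 0.75) = 0.54 SD.

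These half-widths are for an unadjusted comparison at follow-up. Adjusting for baseline setting means might narrow them; it would not change the allocation counts.

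**The case against.** The strongest defence is that 14.3 plans no test. The questionnaire comparison is labelled descriptive, 14.1 calls the analyses mainly descriptive, and the EQ-5D-5L sentence says only that differences will help the team consider the matter, with no threshold and no rule for keeping or dropping an instrument. Much of this stands, and it rules out several stronger readings.

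- A reader might infer that 14.3 contradicts 12.3. It does not: 12.3 disclaims power to test effects, and a descriptive comparison is compatible with that. There is a tension, because judging whether an instrument can capture impact is an inference about effect even when no test is run.
- A reader might infer that the arm difference is the only basis for judging either instrument. It is not: 14.1 and 14.3 also supply completion, floor and ceiling effects, and qualitative work on what the instruments miss.
- A reader might infer that the choice of cost-utility analysis, or of an added valuation exercise, would be settled by noise. The decision text in 14.3 does not name the arm difference, and the economic design is not among the progression criteria in 5.3.
- A reader might take it as stated that there is one control per country and per type. That is only an inference from the stratification.

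It is also fair that ICC, cluster size and SD are assumed, so the exact half-widths are not firm. Finally, one may say that the choice of assessment method belongs in the statistical analysis plan. That would answer a missing detail, but here the protocol itself states a basis, and that basis is unsound.

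**Conclusion.** The point holds in a limited form. For the EQ-5D-5L in full and the resource-use questionnaire in part, 14.3 uses an arm difference as evidence about the instrument, and four versus two settings with no known effect cannot supply that evidence in either direction.

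The firm part uses protocol inputs only: at most 15 allocations, so no randomisation p-value below 0.067. The 0.20 figure depends on the reading of the stratification. The half-width of about 0.2 to 0.6 SD depends on the assumed ICC and cluster size, but the comparison is imprecise across the whole grid. The documents support calling this a poorly chosen criterion beside several sound ones. They do not support calling it a contradiction or a flaw that decides the Phase III economic design. It is worth correcting because the sound criteria are already in the protocol and the weak one can go without loss.

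**What to change.** Amend 14.3 to say three things:

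1. EQ-5D-5L and resource-use responses will be reported by arm and by setting for description only.
2. Arm differences will not be used to retain or drop either instrument, or to choose between cost-utility analysis and another measure of effectiveness.
3. Suitability will be judged on pooled data: completeness, distribution (proportion at full health for the EQ-5D-5L, proportion with zero use for the questionnaire), and the qualitative work already planned.

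Optionally, add a pooled within-setting known-groups contrast, such as students with and without DRV victimisation. It should be presented as supporting evidence that the EQ-5D-5L discriminates between groups. It does not show responsiveness to the intervention, so its precision cannot be set against that of the arm difference as if both answered one question.

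The cost is wording in the protocol, carried into the analysis plan. The main change needs no new data, since completeness, distribution and qualitative findings are already to be collected. By-arm tables remain available to the Phase III team as description.

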15.1 Data collection

Optimisation and feasibility testing phase: Facilitated focus groups will be used in the optimisation phase to consult with the stakeholder advisory group, FE students, FE staff and the ALPHA group to gain feedback on the intervention materials. Structured observations, interviews, focus groups and logbooks will be used in the feasibility testing phase to examine the feasibility, acceptability and fidelity of the intervention.

Assessments in pilot cRCT: The proposed outcome measurements will be assessed at two time points. Baseline measures will be assessed prior to randomisation into the two study arms. A second set of measurements will take place 12 months post baseline. Informed by protocols refined in the MRC-funded SaFE and NIHR-funded Filter study, data collections will take place during 3-hour sessions across three days at each FE site. Students will be provided with information sheets and consent forms and once informed consent has been gained, a paper copy of the questionnaire. In the MRC PHIND study, the majority (58%) of questionnaires were completed electronically.[48] However, participants reported a preference for completing questionnaires using pen and paper. To maximise participation, those completing the questionnaire will be offered entry into a prize draw to win an iPad. The baseline survey will occur in Sep/Oct 2020 and follow up 12 months post baseline (Sep/Oct 2021). Trained fieldworkers will attend social areas and lessons and invite students to complete questionnaires.

16. Protocol/GCP non-compliance

The CI will report any non-compliance to the trial protocol or the conditions and principles of Good Clinical Practice to the CTR in writing as soon as they become aware of it.

17. End of Trial definition

The end of the trial will be considered as the date on which the last participant has completed their follow-up assessment or qualitative component. The sponsor will notify the main REC of the end of the trial within 90 days of its completion or within 15 days if the trial is terminated early.

18. Archiving

The TMF containing essential documents will be archived at an approved external storage facility for a minimum of 15 years. The CTR will archive the TMF on behalf of the Sponsor. Essential documents pertaining to the trial shall not be destroyed without permission from the Sponsor. Archiving and access to archive will be managed in accordance with the Standard Operating Procedures of the CTR.

19. Regulatory Considerations

